8.1 Specification, timing and registration of safety parameters

Side effects due to Multigam 5% and Multigam 10% infusion will be reported by the responsible physician and will be registered in the electronic patient record.

8.2 Procedures for registration and reporting of adverse events (AE)

8.2.1 Adverse event reporting

8.2.1.1 Adverse event definition

An adverse event (AE) is any unfavorable medical event in a patient or subject of the treated group during an experiment or study and does not necessarily have a causal relationship with the treatment. It may therefore be, regardless of the cause, a new additional disease, a deterioration of a similar disease, an injury or any additional impairment of the patient's health (including laboratory values). Any deterioration (this is any clinically significant unfavorable change in the frequency or intensity of an already existing condition) must be considered an AE.

8.2.1.2 Severity of the AE

To describe and assess the severity of an AE, the National Cancer Institute - Common Terminology Criteria for Adverse Events (NCI-CTCAE) version 4.03 is being used. For AEs that are not adequately described in the NCI-CTCAE version 4.03, the following scale is used:

Grade 1	Mild	Transient or mild discomfort; no restriction in physical activity; no medical intervention/therapy required
Grade 2	Moderate	Mild to moderate limitation of activity; limited help may be necessary; no or minimal medical intervention/therapy required
Grade 3	Severe	Noticeable limitation of activity; limited help usually needed; medical intervention/therapy required; hospitalization is possible
Grade 4	Life-threatening	Extreme limitation of activity; significant help required; significant medical intervention/therapy required; hospitalization or care in hospital probable
Grade 5	Death	The event results in death.

An AE or suspected adverse reaction (ADR) is "unexpected" if it does not appear in the list of the current Summary of Product Characteristics (SmPC) or if it is not listed on the specificity or severity observed.

Abnormal laboratory values must be reported as AE if medical intervention (transfusion, hydration ...) is required or if the event is deemed clinically significant by the attending physician.

8.2.1.3 Duration

The start and stop date will be reported for all AEs. The start date is the first date when the patient / subject was aware of the AE and the end date is the date when the event was completely resolved or returned to baseline.

8.2.1.4 Causality

The investigator must determine the relationship between the administration of the immunoglobulin replacement therapy and the occurrence of an AE as Not suspected or Suspected via following definitions:

Not suspected	The temporal relationship between the adverse event and the administration of the immunoglobulin replacement therapy is not causal or small, or other medication, therapeutic interventions or underlying disorders provide sufficient explanation for the observed AE.
Suspected	The temporal relationship between the adverse event and the administration of the immunoglobulin replacement therapy is possibly causal and other medication,

	therapeutic interventions or underlying disorders provide insufficient explanation for the observed AE.
--	---

8.2.1.5 Reporting procedure

All AEs are bundled into the eCRF starting from the patient having signed the information and consent form up to and including the last study visit.

All AEs considered to be related to the substitution therapy and all SAEs independent of their relationship must be followed up until they recover, recover with consequences, non-recovery (death by other cause) or death (by the SAE).

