Primary objective	Assess the administration of Multigam 10% compared to Multigam 5% to shorten the infusion time without additional side effects and loss of quality of care.
Secondary objectives	
 • Evaluate the tolerability and infusion related side effects. • Evaluate patient satisfaction. • Evaluate the number of care actions required. • Evaluate nursing staff satisfaction.
Setup	
In this non-interventional, monocentric, observational study, the administration of Multigam 10% will be compared with the standard (Multigam 5%) in patients with a secondary immunodeficiency due to a hematological disorder.
 
Patients who are being treated with Multigam because of

	
their secondary immunodeficiency will be evaluated for inclusion.
 
The last administration of Multigam 5% will serve as a control. During this check, different parameters will be evaluated:
 
 -Infusion time (hours) -Hospitalization time at the oncological day clinic (hours) -Side effects (via CTCAE v4.03) -Nursing staff care actions 
Subsequently, an identical evaluation will take place at the first administration of Multigam 10% and the satisfaction of the patient and the nursing staff will also be assessed. The results will be analyzed and compared.
 
Patients can then receive Multigam 10% or Multigam 5% according to their preference.
  <pre> graph TD A[Screening] --> B["Multigam 5% administration"] B --> C["First evaluation"] C --> D["Multigam 10% administration"] D --> E["Final evaluation"] </pre>
Endpoints	
Primary:
 
To compare the infusion time (hours) and tolerance of Multigam 10% and the standard administration of Multigam 5%.

	
Secondary:
 
 • Assess the tolerance and patient satisfaction of Multigam 5% vs. Multigam 10% via: 
 - Patient questionnaire - Scoring of side effects via CTCAE v4.03 • Assess nursing staff care actions • Assess the satisfaction of the nursing staff (questionnaire) • Patient characterization (age, gender, disorder)
Population	30 patients with a secondary immunodeficiency due to a hematological disorder.

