3.5 Study diagram

3.6 Study flowchart

	Study visit 1 (Multigam 5%)	Study visit 2 (Multigam 10%)
Information and consent form	X	
Physical examination AE scoring via CTCAE (v4.03)	X	X
Patient questionnaire		X
Questionnaire concerning IVIg administration	X	X
Nursing staff questionnaire		X

4. Selection and exclusion of participants

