4.3 Expected duration of study

- Start-up: february 2017
- Recruitment: 4 weeks
- First participant: Q2 2017
- EC submission: Q2 2017
- Final reporting: december 2017

5. Study actions per visit

5.1 Study visit 1

- Sign information and consent form
- Multigam 5% administration
- Questionnaire concerning IVIg administration
- CTCAE v4.03 scoring during and after infusion

5.2 Study visit 2

- Multigam 10% administration
- Questionnaire concerning IVIg administration
- CTCAE v4.03 scoring during and after infusion
- Patient questionnaire
- Nursing staff questionnaire

6. Data collection

The following data will be stored in the eCRF:

- Patient characteristics (age, gender and disorder)
- Infusion time (hours)
- Hospitalization time at the oncology day center (hours)
- Safety reporting (collect AEs en SA's according to CTCAE v4.03 criteria)
- Questionnaire concerning IVIg administration (both visits, annex 2)
- Patient satisfaction questionnaire (last visit; annex 1)
- Nursing staff satisfaction questionnaire (last visit; annex 3)

7. Assessment of efficiency

Primary endpoint:

- **Comparing the infusion time and tolerance**

Evaluate via time measurements, questioning and AE reporting during both treatments

Secondary endpoints:

- **Satisfaction and therapeutic tolerance**
 - Evaluation of satisfaction via questionnaire and tolerance via AE reporting
- **Safety**
 - Evaluate AEs and SAEs via CTCAE v4.03 criteria
- **Care actions**
 - Evaluate the number of nursing actions per patient
- **Satisfaction of nursing staff**
 - Evaluation of satisfaction via questionnaire
- **Patient characterization**
 - Characterization of patients (age, gender, disorder)

8. Assessment of safety

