8.2.2 Serious Adverse Event reporting

A serious adverse event (SAE) is any AE that meets one of the following criteria:

- death
- life-threatening (this is when, according to the researcher, the patient is exposed to a direct risk of dying from the AE)
- requires hospitalization of patient or extension of existing hospitalization (hospitalization is defined as hospitalization of patient in hospital, regardless of length of stay)
- results in persistence of significant incompetence (a substantial disruption in the patient's ability to perform normal life functions)
- forms an important medical event

Important medical events are defined as events that do not directly threaten the life of the patient or result in death, hospitalization or incompetence, but which do endanger the patient or require medical or surgical intervention to avoid one of the consequences above.

Each SAE, independent of the causal link, that occurs after the patient has signed the information and consent form until the last study visit, must be reported to the sponsor. Each SAE report must be reported to the sponsor within 24 hours of awareness and also by using the Serious Adverse Event form in the eCRF.

9. Statistics

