Annex 1: Patient questionnaire

	Strongly disagree (1)	Disagree (2)	Neutral (3)	Agree (4)	Strongly agree (5)
I experienced fewer side effects with Multigam 10%					
I experienced time gain with Multigam 10%					
I will therefore have a more productive day					
For my own situation I am in favor of using Multigam 10%					

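### Adverse event collection stops at the Multigam 10% visit, so reactions to 10% that start later are not systematically collected

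*Combined protocol and SAP*

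**What the plan says.** The primary objective in the synopsis is to "shorten the infusion time without additional side effects and loss of quality of care", and tolerance is part of the primary endpoint (3.2).

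- **Collection window.** AEs enter the eCRF "starting from the patient having signed the information and consent form up to and including the last study visit" (8.2.1.5). An SAE is reportable if it "occurs after the patient has signed the information and consent form until the last study visit" (8.2.2).
- **Last visit.** The flowchart (3.6) has two columns: visit 1 with 5% and visit 2 with 10%. Section 5.2 lists the infusion, the scoring and the questionnaires for visit 2. No later visit, call or diary appears. The synopsis then leaves patients free to receive either product.
- **Scoring at visits.** Sections 5.1 and 5.2 both list "CTCAE v4.03 scoring during and after infusion". The synopsis says that "an identical evaluation will take place at the first administration of Multigam 10"%. No section says how long the period after infusion lasts or when a visit ends.
- **Follow-up.** Section 8.2.1.5 follows related AEs and all SAEs to outcome.
- **Other routes.** Section 8.1 has the physician register side effects of either product in the electronic patient record, with no time limit. The patient questionnaire item "I experienced fewer side effects with Multigam 10"% is completed at visit 2 (3.6, 5.2).

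**The concern.** The study's last observation of 10% is the visit at which it is first given. A reaction that begins afterwards, including a serious one, has no planned route into the study data. The follow-up rule does not help, because it applies to events already recorded and does not add new onsets. The questionnaire item does not help either, because it is answered before a late reaction could occur.

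The 5% infusion is treated differently. Consent is signed at visit 1, so an event that starts after that infusion remains eligible until visit 2, although no section says that patients are asked about it.

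Two things are at stake. One is the primary claim of no added side effects. The other is the safeguard in 9.1, which extends the sample if 10% turns out to cause more side effects. Both would rest on data in which late reactions to 10% appear only by chance.

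**Working it through.** **The plan's own figure.** Section 9.1 sets 30 patients and calls this enough to pick up mild side effects. It gives no reaction rate, power or margin, so the figure cannot be reproduced. The calculations below are illustrations.

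**Inputs.** From the plan: n = 30 (9.1), infusions every 3 to 4 weeks (section 2), recruitment of 4 weeks (4.3) and a 2-month maximum (synopsis). Assumed, because the documents give neither: p, the share of patients who react to an infusion, and f, the share of those reactions that start after the visit. Eligibility requires good tolerance of 5%, which suggests a low p on 5% but gives no rate for 10%. I use p = 3% and 10%, and f from 0 to 75%.

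**Step 1: the windows.** For 5%, eligible onset runs from visit 1 to visit 2, which is 21 to 28 days if visits follow the dosing interval. For 10%, it is visit 2 only.

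**Step 2: late reactions to 10% that are missed.** Expected number = 30 × p × f. Chance of missing at least one = 1 − (1 − p × f)^30. Example for p = 10%, f = 25%: 30 × 0.10 × 0.25 = 0.75, and 1 − 0.975^30 = 53.2%.

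| f | Expected missed, p = 3% | Chance of at least one, p = 3% | Expected missed, p = 10% | Chance of at least one, p = 10% |
|---|---|---|---|---|
| 0 | 0 | 0% | 0 | 0% |
| 5% | 0.045 | 4.4% | 0.15 | 14.0% |
| 10% | 0.09 | 8.6% | 0.30 | 26.0% |
| 25% | 0.225 | 20.2% | 0.75 | 53.2% |
| 50% | 0.45 | 36.5% | 1.50 | 78.5% |
| 75% | 0.675 | 49.5% | 2.25 | 90.4% |

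**Step 3: what 30 patients can detect.** With a full window, the rate that gives a 95% chance of at least one reaction is 1 − 0.05^(1/30) = 9.5%. If collection ends at the visit, the overall rate must be 9.5% / (1 − f): 10.0%, 10.6%, 12.7%, 19.0% or 38.0% for f = 5%, 10%, 25%, 50% or 75%. Likewise, zero reactions in 30 gives a one-sided 95% upper bound of 9.5%, and that bound applies only to reactions that start at the visit.

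**Step 4: only if all eCRF AEs were counted by product.** Take equal true rates of 10%, and suppose that reactions after visit 1 are reported at visit 2. Then 5% would show 30 × 0.10 = 3.0 reactions and 10% would show 30 × 0.10 × (1 − f): 2.85, 2.70, 2.25, 1.50 or 0.75 for the same values of f. Under matched visit scoring this difference does not arise.

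**Step 5: room in the calendar.** If the 2-month maximum is per patient, two dosing intervals take 42 to 56 days of the 59 to 62 available. If it is for the whole study, recruitment plus one interval takes 28 + 21 = 49 to 28 + 28 = 56 days, leaving 59 − 56 = 3 to 62 − 49 = 13 days.

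**The case against.** The strongest reply is about scope. The side effects named in the secondary objectives, the rationale and 3.1 are infusion-related, section 7 ties AE reporting to the two treatments, and the scoring is the same at both visits. On that reading the study compares acute tolerability around the infusion, and late onset is another question. Part of this stands: the matched scoring is a fair comparison of what it covers. But no section limits infusion-related effects to onset at the visit, the causality rule in 8.2.1.4 has no onset limit, and 8.2.1.5 keeps the whole interval after 5% open. If acute tolerability was meant, the plan and report should say so.

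A reader might go further than the documents allow in four ways.

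- **That the comparison is biased towards 10%.** This needs all eCRF AEs to be pooled by product. Sections 7 and 9.2 neither state nor rule that out, and the identical evaluation in the synopsis points away from it.
- **That a late reaction could never come to light or prompt the 9.1 extension.** Section 8.1 has no time limit, and the 9.1 rule is not restricted to eCRF entries. Capture is passive and incomplete, but possible.
- **That observation ends exactly at discharge.** The end of the visit is undefined, and the synopsis shows a final evaluation after the 10% infusion without a time.
- **That many reactions are being lost.** Nothing in the documents says how often late reactions occur. With f at 5% or 10% the losses are modest.

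Sections 8.2.1.5 and 12 already require events found within the window to be entered in the eCRF. The gap concerns onsets after visit 2.

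**Conclusion.** The point holds. Under the stated rules, new reactions to 10% that start after visit 2 are not systematically collected, while those after the 5% visit remain eligible until visit 2. The matched visit scoring is unbiased by window, but it supports the primary claim only for reactions seen at a visit whose end is not defined. A favourable imbalance for 10% follows only if AEs are counted by product over the whole eCRF.

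The size cannot be determined from the documents. At an assumed 10% rate, the chance of missing at least one late reaction runs from 0% if none start late to 90% if three quarters do; at 3% it runs from 0% to 50%. These figures depend wholly on the assumed p and f. The conclusion about the window rests on the text alone. It should be fixed, because tolerance is a primary endpoint and the remedy is cheap.

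**What to change.** 1. In 8.2.1.5 and 8.2.2, replace the last study visit as the end point with one fixed window of equal length after each infusion, no longer than the shortest dosing interval (3 weeks). Ask the same questions for both products: for 5% at visit 2 before the 10% infusion starts; for 10% at the next routine infusion, or by one call or chart check if none falls in time. Eligibility requires a need for only two infusions, so a third cannot be taken for granted. Enter side effects found in the patient record within the window in the eCRF.
2. In sections 7 and 9.2, state that primary tolerance compares the two products over that same window and does not pool all eCRF AEs by product.
3. If collection is not extended, limit the tolerance conclusion to the matched visit scoring and report that later-onset reactions were not systematically assessed.

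**Cost.** A short amendment and up to 30 brief checks, in a study described as non-interventional. If the 2-month maximum is per patient, even a 3-week window fits. If it covers the whole study, the 3 to 13 days left allow only a short window, or the limit must be restated. Option 3 needs no added data collection.

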8.2.2 Serious Adverse Event reporting

A serious adverse event (SAE) is any AE that meets one of the following criteria:

- death
- life-threatening (this is when, according to the researcher, the patient is exposed to a direct risk of dying from the AE)
- requires hospitalization of patient or extension of existing hospitalization (hospitalization is defined as hospitalization of patient in hospital, regardless of length of stay)
- results in persistence of significant incompetence (a substantial disruption in the patient's ability to perform normal life functions)
- forms an important medical event

Important medical events are defined as events that do not directly threaten the life of the patient or result in death, hospitalization or incompetence, but which do endanger the patient or require medical or surgical intervention to avoid one of the consequences above.

Each SAE, independent of the causal link, that occurs after the patient has signed the information and consent form until the last study visit, must be reported to the sponsor. Each SAE report must be reported to the sponsor within 24 hours of awareness and also by using the Serious Adverse Event form in the eCRF.

9. Statistics

9.1 Sample size

For this descriptive, semi-quantitative study, the sample size is determined on 30 patients. Based on data in the package leaflet, we expect that the infusion time for Multigam 10% will be shorter than for Multigam 5%. This sample size will also be sufficient to correct for any variability as a result of nursing activities. A sample of 30 patients is sufficient to detect mild side effects. If, unexpectedly, more side effects occur with Multigam 10% administration, we will extend the sample size through an amendment and investigate this further. To evaluate the satisfaction of the patients and the nursing staff, 30 patients are also sufficient to correct for any missing values.

9.2 Analysis

The results are reported quantitatively (number of care actions, infusion and hospitalization time) and qualitatively (patient and nursing staff satisfaction). For the number of care actions, infusion time and hospitalization time, a T-test will examine whether both datasets (Multigam 5% and Multigam 10%) differ significantly from each other. The 95% confidence interval will also be determined and Cohen's d will be calculated to estimate the magnitude of the difference between the two variables (effect size, estimate the strength of the difference). For the satisfaction of patients and nursing staff, descriptive statistics will be used.

10. Direct access to source data and documents

The researcher / institution will provide direct access to source data and other documents. This access can consist of study-related monitoring, audits, EC review and statutory inspections.

11. Ethical and regulatory compliance

The research will be conducted in accordance with the principles of the Helsinki Declaration (current version), the principles of GCP and in accordance with the appropriate legal requirements. This protocol and all related documents will be submitted for review by the Ethics Committee.

The research will be conducted in accordance with the principles of the Helsinki Declaration (current version), the principles of GCP and in accordance with the appropriate legal requirements. This protocol and all related documents will be submitted for review by the Ethics Committee.

The study can and will only be conducted on the basis of prior consent, by the patient or the legal representative, to participate in the study. The participating site will obtain a signed informed consent

document (ICD) for each patient before registering patients and taking part in the study in accordance with the prevailing legislation, regulations and, if necessary, the approval of the (local) Ethics Committee. The participating site will retain the ICDs in accordance with the requirements of the relevant regulatory bodies and laws.

The researcher and the participating site will treat all information and data related to the study as confidential and will not disclose such information to third parties or use the information for any other purpose than the execution of the study. The collection, processing and disclosure of personal data, such as the health of patients and medical information, is subject to compliance with the prevailing protection and processing of personal data (Directive 95/46 / EC and Belgian law of December 8, 1992 on the protection of Secrecy in connection with the Processing of Personal Data).

With **coded** data, a link remains between the data and the individual who provided the information. The research team is obliged to protect the data against disclosure outside the research in accordance with the terms of the research protocol and the informed consent document. The patient name or other items that can be used for identification must be stored separately from the research data and replaced with a unique code to create a new identity for the patient. Note that encrypted data is not anonymous.

12. Data handling and management

As part of the responsibilities associated with participation in the study, the researcher agrees to maintain accurate eCRFs and source documents. The researcher or delegate must enter all results collected during the study into eCRFs.

13. Publication policy

The results of this study will be published as an abstract or article in which a co-authorship is offered to everyone who has made a significant contribution to the writing of the protocol, the execution of the study and the processing and interpretation of the results. The principal investigator has final responsibility concerning the publication.

14. Insurance/compensation

In accordance with the Belgian legislation on experiments on human persons of May 7, 2004, the Sponsor will without fault assume the responsibility of any damage to a study patient, both directly and indirectly related to participation in the study, and will compensate provide through their own insurance.

15. Financial aspects

Both Multigam 5% and Multigam 10% are commercially available and are prescribed according to the formulary.

16. References

Chinen, J. and Shearer, W. (2008) '6. Secondary immunodeficiencies, including HIV infection', *Journal of Allergy and Clinical Immunology*, 121(2), pp. S388–S392. doi: 10.1016/j.jaci.2007.06.003.

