3.2 Primary endpoints

Comparing the infusion time (hours) and tolerance between Multigam 10% and the standard administration.

[figure not shown]

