3.3 Secondary endpoints

- Assess the satisfaction and therapeutic tolerance of Multigam 5% vs. Multigam 10% via:
 - Patient questionnaire
 - CTCAE v4.03
- Assess the care actions of the nursing staff
- Assess the satisfaction of the nursing staff (questionnaire)
- Patient characterization (age, gender, disorder)

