Annex 2: Questionnaire concerning IVIg administration (to be filled in by nursing staff)

	Multigam 5%
Infusion time (..hour..minutes)	Start: h min Stop: h min
Number of care actions	
	Multigam 10%
Infusion time (..hour..minutes)	Start: h min Stop: h min
Number of care actions	

Care action means both the increase or decrease of infusion rate and any other intervention due to intolerance / complication.

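### Tolerance is named as part of the primary endpoint, and again as secondary, but section 9.2 plans no CTCAE-based estimate or confidence interval for it

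*Combined protocol and SAP*

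**What the plan says.** Section 3.2 gives the primary endpoint as "Comparing the infusion time (hours) and tolerance between Multigam 10% and the standard administration", and the synopsis agrees. Section 7 says how the primary endpoint will be assessed: "Evaluate via time measurements, questioning and AE reporting during both treatments". The primary objective in the synopsis is "to shorten the infusion time without additional side effects and loss of quality of care".

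Tolerance also appears at the secondary level. The synopsis lists "Evaluate the tolerability and infusion related side effects" as a secondary objective. Section 3.3 has "Assess the satisfaction and therapeutic tolerance of Multigam 5% vs. Multigam 10% via" a patient questionnaire and CTCAE v4.03, and section 7 repeats tolerance under the secondary endpoints.

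Sections 5.1 and 5.2 schedule CTCAE scoring during and after the infusion at both study visits.

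Section 9.2 opens with "The results are reported quantitatively (number of care actions, infusion and hospitalization time) and qualitatively (patient and nursing staff satisfaction". It then assigns a t-test, a 95% confidence interval and Cohen's d to care actions, infusion time and hospitalization time, and descriptive statistics to satisfaction. Nothing is assigned to adverse events.

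Section 9.1 sets the sample at 30 and states "A sample of 30 patients is sufficient to detect mild side effects". It adds that the sample will be extended by amendment if side effects turn out more frequent on the 10% product, without defining what counts as more frequent.

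**The concern.** Half of the named primary endpoint has no planned summary measure, while hospitalization time, which is in neither endpoint list, has three statistics. The gap is the same whether tolerance is primary or secondary.

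Two things are at stake. First, the grade cut-off, the causality filter and the time window could all be chosen after the data are seen. Second, similar raw counts on the two products could be read as meeting the objective of no extra side effects, although 30 pairs leave a sizeable increase open. The extension rule in 9.1 also depends on a comparison that the plan never defines.

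**Working it through.** **Is there an analysis elsewhere?** Three places come close.

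- Section 7 names data sources (time measurements, questioning, AE reporting) but no summary measure. The synopsis says only that results will be analysed and compared.
- Care actions are tested, but Annex 2 defines them broadly: "Care action means both the increase or decrease of infusion rate and any other intervention due to intolerance / complication". The count mixes rate adjustments with interventions for intolerance and is not graded by CTCAE.
- One item in Annex 1 asks patients whether they had fewer side effects on the 10% product. Disagreement can mean the same or more, and more is the outcome of interest.

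None of these gives a CTCAE-based proportion, difference or interval.

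**The plan's own figure.** The sample of 30 cannot be reproduced, because section 9.1 gives no incidence, effect size, standard deviation or power. What 30 patients deliver can be calculated.

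**Paired comparison.** Inputs: n = 30 patients, each seen on both products (section 9.1 and the study visits), and 95% confidence (the level used in 9.2 for other outcomes). Let b be the number of patients with an AE on 10% only and c the number with an AE on 5% only. The documents give no event rates, so b and c are assumptions.

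The Tango paired score limits are the values of Δ (10% minus 5%) at which

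T(Δ) = (b − c − nΔ) / √{n[2q + Δ(1 − Δ)]} = ±1.96,

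where q is the constrained estimate of the 5%-only probability:

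q = [√(B² − 4AC) − B] / (2A), with A = 2n, B = −b − c + (2n − b + c)Δ, C = −cΔ(1 − Δ).

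- No discordant patients (b = c = 0): q = 0 and the limit reduces to z²/(n + z²) = 3.841/33.841 = 11.4 points.
- Three each way (b = c = 3): at Δ = 0.1817, q = 0.0546. The numerator is −5.451 and the denominator is √(30 × [0.1091 + 0.1487]) = 2.781. The ratio is −1.96, so the limit is 18.2 points.

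| Discordant patients (10% only, 5% only) | Difference | 95% interval, points |
|---|---|---|
| 0, 0 | 0 | −11.4 to 11.4 |
| 1, 1 | 0 | −14.0 to 14.0 |
| 3, 3 | 0 | −18.2 to 18.2 |
| 5, 5 | 0 | −21.5 to 21.5 |

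These rows are examples, not bounds.

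**The sufficiency sentence in 9.1.** Suppose that to detect a side effect means seeing at least one case. The probability is then 1 − (1 − p)^30:

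- p = 10%: 1 − 0.0424 = 96%
- p = 5%: 1 − 0.2146 = 79%
- p = 2%: 1 − 0.5455 = 45%

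A probability of 95% requires p = 1 − 0.05^(1/30) = 9.5%. If no case is seen in 30, the exact two-sided 95% upper limit is 1 − 0.025^(1/30) = 11.6%.

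**The case against.** The study calls itself descriptive and is non-interventional. The synopsis lists CTCAE side effects among the parameters evaluated at both infusions, section 7 assigns AE reporting to the primary endpoint, and section 9.1 gives an excess of side effects a consequence. The comparison and its data are therefore intended; only the summary measure and interval are missing. That is fair, and it lowers the severity. It does not remove the gap, since 9.2 gives an interval to other outcomes and none to this one. No hypothesis test or power calculation for tolerance is being asked for.

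Three stronger readings are tempting, and the documents do not support them.

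- *The 5% count is zero by design, because eligibility requires tolerated 5% infusions and the last 5% infusion is the control.* This needs the control to be one of the two qualifying infusions. The study is described as prospective, the synopsis diagram places screening before the 5% administration, and the flowchart and section 5.1 put consent and the 5% infusion at visit 1. These fit a control infusion given after the qualifying ones, although no sentence says so. What stands is that eligibility selects patients who tolerated the 5% product, which can tilt the difference against 10%.
- *The follow-up windows are unequal, because section 8.2.1.5 collects AEs from consent to the last visit.* That is a general safety-collection rule. Sections 5.1 and 5.2 already schedule matching scoring at each infusion, so the imbalance arises only if an analyst pools every AE.
- *Thirty patients are too few, or the sentence in 9.1 is false.* Without an incidence it is unsupported, not shown to be wrong, and counting at least one case is only one reading of what detection means.

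**Conclusion.** The concern holds in a limited form. Tolerance has an unclear rank, primary in some places and secondary in others, and in neither role does 9.2 plan a CTCAE-based estimate or interval. Raw counts alone could not support a statement of no additional side effects: equal counts in 30 pairs remain compatible with a rise of about 11 points with no discordant patients, or about 18 with three each way. Those figures rest on complete pairs, the 95% paired score method and assumed discordant counts.

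This should be fixed, but it does not invalidate a descriptive study: the data are already collected and the intent to compare is stated. The sufficiency sentence in 9.1 is a minor wording matter and carries none of the weight.

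**What to change.** 1. State once, consistently across the synopsis and sections 3.2, 3.3 and 7, whether tolerance is primary or secondary. The estimate below is needed either way.
2. Add one main tolerance estimate to 9.2: for each product, the number and proportion of patients with at least one AE of any grade scored during and after the infusion at the study visit, with the same window for both. Report the paired difference, 10% minus 5%, with a 95% paired confidence interval (score or exact). Grade 2 or higher, and AEs classed as Suspected under section 8.2.1.4, are supportive. Any statement of no additional side effects should quote the upper limit. The extension sentence in 9.1 should refer to this same estimate.
3. Note beside the estimate that eligibility selects patients who tolerated the 5% product, which can tilt the difference against 10%. Say whether the control infusion is one of the two qualifying infusions. The synopsis eligibility criteria carry a grade threshold for side effects and sections 4.1 and 4.2 do not; these passages must be reconciled.
4. Qualify the 9.1 sentence, for example: 30 patients give at least 95% probability of seeing one or more cases of a side effect whose incidence is 9.5% or higher (79% at 5%), and 0 of 30 is compatible with an incidence up to 11.6% (two-sided 95%).

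The cost is a few sentences and one small table, with no extra patients or data. The drawbacks are a wide interval, a less favourable statement of sensitivity, and a visit-day window that misses reactions starting later.
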